10.5.4 Best Overall Response

It is the best response, as assessed and confirmed by site PI, from the start of the treatment until disease progression or discontinuation from the study.

This data will be summarized using frequency and percentage for Complete Response (CR), Partial Response (PR), Stable Disease (SD), and Progressive Disease (PD), as reported in the CRFs for overall subjects.. This data will also be listed.

10.5.5 Progression Free Survival (PFS)

It is defined as time of the first dose of Tenalisib to disease progression or death. Subjects who die without a reported prior progression will be considered to have progressed on the date of

their death. Subjects who did not progress or die will be censored on the date of their last tumor assessment that will be assessed at End of Treatment visit for this study. End of treatment visit will be considered as the cut-off visit for the calculation of PFS.

This data will be summarized using the Kaplan-Meier method and displayed graphically for overall subjects. The following reports will be generated:

- The Q1, median and Q3 PFS time will be provided along with 95% CI for the Q1, median, and Q3 PFS time will be presented for the Overall subjects using Brookmeyer-Crowley method, subjected to availability of adequate data.
- The number and % of patients with disease progression (further divided into disease progression or death) will be provided.
- The number and % of patients censored (further divided by reasons for censoring) will be provided.
- Kaplan-Meier curves will be produced.
- A listing of PFS data will be provided.

10.6 Safety Analysis

Analysis Set: Safety

The safety analyses will be reported for Overall patient data only.

10.6.1 Treatment Exposure and Compliance

Analysis set: Safety

Treatment compliance and the treatment exposure will be summarized descriptively (n, mean, median, standard deviation, minimum and maximum values) and will also be listed.

- The treatment exposure to the study medication for subject will be calculated as:
$$\text{Exposure (day)} = \text{Last day of dosing} - \text{First Day of dosing} + 1$$
 - A summary of duration of treatment (days) will be provided. In addition, a plot for duration on treatment will be provided per patient.
- The treatment compliance percentage (per patient), which is reported in the eCRF, will be summarized descriptively per Cycle. This data will be listed for individual patient.

10.6.2 Adverse Events

Analysis set: Safety

Note: If needed, adverse event data may be presented for all screened patients.

The frequency of adverse events (AEs) will be computed by counting each patient only once per MedDRA [Version 23.0 (Hierarchy) or higher] preferred term and according to the maximum NCI CTCAE v.5.0 grade attained by the patient over the specified period. The percentage of

patients with an event will be calculated using the number of patients in the safety analysis set as the denominator.

Standard Summaries of Adverse Events

Treatment Emergent Adverse Events (TEAEs) are those that start on or after the date of first dose of study medication.

An overall summary of TEAEs (number and percentage of patients along with the number of events) will be presented with the following:

- Any non-TEAE
- Any TEAE
- Treatment Related TEAEs
- Serious non-TEAEs
- Serious TEAEs
- Treatment Related Serious TEAEs
- Grade 3 or 4 TEAEs
- Treatment Related Grade 3 or 4 TEAEs
- TEAEs leading to discontinuation
- Treatment Related TEAEs leading to discontinuation
- Serious TEAEs leading to discontinuation
- Treatment Related Serious TEAEs leading to discontinuation
- TEAEs leading to dose interruptions/dose reductions
- Fatal TEAEs
- Treatment Related Fatal TEAEs
- Protocol-Defined Adverse Events of Special Interest:
 - Pregnancy, abortion, birth defects/congenital anomalies
 - Overdose

Summaries showing the number of patients (n, %) along with number of events by SOC and PT will be provided for the following:

- TEAEs (Related/ Not Related/ Total)
- Grade 3, 4 and 5 TEAEs (Related/ Not Related/ Total)
- Treatment-Emergent SAEs (Related/ Not Related/ Total)
- TEAE with maximum CTCAE grade
- Treatment-Related TEAEs with maximum CTCAE grade
- Deaths

The adverse events data will also be listed for individual patients.

- Any non-TEAE
- AEs
- Related TEAEs
- Treatment Emergent Grade 3, 4 and 5 AEs
- Treatment Related Grade 3, 4 and 5 AEs
- SAEs

- Treatment Related SAEs
- TEAE leading to discontinuation

10.6.3 Clinical Laboratory Tests

Analysis Set: Safety

Laboratory data will be presented per cycle.

The baseline measurement is the last pre-treatment measurement taken on or before Cycle 1 Day 1.

Absolute values of Laboratory parameters will be presented using descriptive statistics (n, mean, median, standard deviation, minimum and maximum values) as appropriate.

The laboratory data will also be listed.

A separate listing of patients with abnormal laboratory test values will also be presented.

Hematology	Chemistry Panel I	Chemistry Panel II	Urinalysis	Other
Hematocrit	Total bilirubin	Blood glucose	Blood	PT
Hemoglobin	Alkaline phosphatase	LDH	Glucose	INR
Platelet count	Alanine aminotransferase	Albumin	Protein	
White blood cell count	Aspartate aminotransferase	Total protein	Specific gravity	
WBC (Total and differentials)	Urea or blood urea nitrogen	Total Cholesterol	Microscopic exam	
Red blood cell count	Creatinine	Triglyceride (TG)		
Absolute neutrophil count	Gamma-glutamyl transferase	LDL		
Absolute lymphocyte count	Sodium	HDL		
	Potassium	TSH		
	Calcium	T3 (Total or Free)		
	Phosphorous	T4 (free)		
	Carbon Dioxide (CO₂) or bicarbonate			
	Chloride			
	Magnesium			

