7.5.3 Abnormal laboratory values

Any grade 3/4 laboratory abnormalities or any clinically significant grade 1/2 hematology or biochemistry laboratory value(s) should be recorded as an AE. Isolated laboratory abnormality without clinical significance should not be captured as AE if confirmed by the investigator. If an abnormal laboratory value or vital sign is associated with clinical signs and/or symptoms, the sign or symptom should be reported as an AE, and the associated laboratory value or vital sign should be considered additional information that must be collected on the relevant CRF. If the laboratory abnormality is a sign of a disease or syndrome, only the diagnosis needs to be recorded on the SAE Report Form or AE CRF.

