9.4.2 Safety analyses

The safety endpoints will include:

- Incidence of AEs and AEs considered to be drug-related
- Incidence of grade 3, grade 4 AEs
- Incidence of SAEs and death
- Laboratory values
- ECG/vital signs

The safety endpoints will be listed and/or summarized. No inferential statistical analyses will be performed.

The analyses of safety will be based on the frequency of adverse events and their severity for patients in each portion who received at least one dose of study treatment. Worst toxicity grades per patient will be tabulated for select adverse events and laboratory measurements by using NCI CTCAE criteria v5.0 with exceptions for platelet, hemoglobin and ANC that are recommended by iwCLL guidelines for the CLL.

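### SAP 10.6.3 omits, without a stated reason, the per-patient worst-grade laboratory table promised in protocol 9.4.2, including its iwCLL grading of platelets, hemoglobin and ANC

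*SAP*

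**What the plan says.** Protocol 9.4.2 (Safety analyses) states: "Worst toxicity grades per patient will be tabulated for select adverse events and laboratory measurements by using NCI CTCAE criteria v5.0", and continues "with exceptions for platelet, hemoglobin and ANC that are recommended by iwCLL guidelines for the CLL". Protocol 7.4 sets out those exceptions. Platelets and hemoglobin are graded by percentage decrease from baseline, and ANC by absolute nadir. Footnotes make some patients with low baseline platelet or neutrophil counts not evaluable.

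SAP 10.6.3 (Clinical Laboratory Tests) plans the following:
- "Laboratory data will be presented per cycle".
- "Absolute values of Laboratory parameters will be presented using descriptive statistics", namely n, mean, median, SD, minimum and maximum.
- A full laboratory listing, and "A separate listing of patients with abnormal laboratory test values will also be presented".
- A definition of baseline, but no change, shift or grade that uses it.

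SAP 10.6.2 keeps the adverse event half of the commitment. It tabulates treatment-emergent events by maximum CTCAE v5.0 grade, and Grade 3 to 5 events, by system organ class and preferred term. SAP 4.2 also names CTCAE v5.0. The SAP cites iwCLL for response but not for toxicity.

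Protocol 7.5.3 governs how laboratory values become adverse events. Grade 3/4 abnormalities, and Grade 1/2 values that are clinically significant, should be recorded. It then adds: "Isolated laboratory abnormality without clinical significance should not be captured as AE if confirmed by the investigator".

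**The concern.** A specific protocol commitment has no counterpart in the SAP, and the SAP does not say why. Its introduction reserves a general right to modify the protocol's plans. Protocol section 9 has the study report discuss deviations from the SAP, so a departure made in the SAP itself need not be explained anywhere.

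The omission concerns toxicities that the protocol singles out. Protocol 3.5.5 names raised ALT/AST and neutropenia as events reported with Tenalisib, and the background section lists Grade 3 transaminitis among the dose-limiting toxicities of the earlier US study. Characterising safety is a secondary objective. Without the table, no planned summary says how many patients reached each laboratory grade independently of what the investigator chose to record as an adverse event.

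**Working it through.** No sample size, power or alpha figure is at issue. The check compares the protocol's promise with each planned SAP output, and uses two small illustrations. All ALT and platelet values in them are assumed.

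**1. Can per-cycle absolute values give a per-patient grade count?**
Inputs: 21 patients enrolled (SAP section 6), assumed all dosed and all measured at each cycle; ALT at 0.6 x ULN, except for one value of 10 x ULN in a cycle; normal baseline. In protocol Table 5, ALT above 5 and up to 20 x ULN is Grade 3.
- Mean in an affected cycle = (20 x 0.6 + 1 x 10)/21 = 22/21 = 1.05 x ULN.
- Median = 0.6 x ULN; maximum = 10 x ULN.

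Suppose four cycles show this summary. If one patient accounts for all four, the worst-grade rate is 1/21 = 4.8%. If four different patients peak once each, it is 4/21 = 19.0% (exact 95% interval 5.4% to 41.9%). Two or three patients would give 9.5% or 14.3%. The four per-cycle tables are identical in every case, including the maximum. They reveal that a high value occurred, but not in how many patients.

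**2. Can absolute values stand in for iwCLL grades?**
Take two patients who both reach platelets of 40 x 10^9/L. Both assumed starting values satisfy the platelet entry criterion.
- From 60: fall = (60 - 40)/60 = 33%, Grade 2 in protocol 7.4 (25 to 49%).
- From 160: fall = (160 - 40)/160 = 75%, Grade 4 (75% or more).

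The SAP summary treats the two alike. Baselines can be expected to differ, because inclusion criterion 7 admits patients with counts below the limits when marrow involvement is the cause. ANC is graded on absolute values, but baseline still matters: a patient below 1 x 10^9/L before therapy is not evaluable for that toxicity.

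**3. Do the adverse event tables fill the gap?**
Only in part. Grade 1/2 laboratory values enter only if judged clinically significant. For Grade 3/4 values, protocol 7.5.3 requires recording, but its next sentence exempts isolated abnormalities judged not significant and states no grade limit. It can be read as qualifying all grades or only the lower ones. On either reading the count rests on investigator recording in an open-label, single-arm trial. Grades in those tables are described as CTCAE v5.0, with no iwCLL exception.

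**4. Unscheduled values.**
Table 1 footnote 8 allows unscheduled chemistry tests, and protocol Tables 4 and 5 call for weekly or twice-weekly monitoring during several of these toxicities, so peaks may fall between scheduled visits. SAP 10.6.3 does not say whether such values enter the per-cycle statistics.

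**The case against.** A reader might infer that the SAP reports nothing but per-cycle averages, that liver or blood toxicity could therefore be hidden, and that the safety objective would be answered from listings alone. The documents do not support this. The per-cycle statistics include minimum and maximum, so in the ALT illustration the value of 10 x ULN is on the page. The abnormal-value listing should show each affected patient. A Grade 3 ALT should normally be recorded as an adverse event under protocol 7.5.3, and would then appear in the maximum-grade and Grade 3 to 5 tables of SAP 10.6.2.

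Three further points deserve weight. The trial closed after Stage 1 with 21 patients enrolled, so listings can be read case by case. The SAP is silent on unscheduled values; it does not exclude them. And protocol 9.4.2 promises neither change from baseline nor a shift table, and leaves the choice of parameters open.

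All of this stands and limits the consequence. It does not remove the discrepancy. A listing leaves the reader to do the grading and counting that the protocol promised as a table, and the general permission to modify the protocol's plans gives no reason for this change.

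**Conclusion.** The point holds as an unexplained omission. The laboratory half of the worst-grade commitment in protocol 9.4.2 is absent from SAP 10.6.3, and the iwCLL exceptions for platelets, hemoglobin and ANC appear nowhere in the SAP's toxicity grading. Planned outputs cover the gap in part. What remains uncovered is a count of patients by worst laboratory grade that does not depend on adverse event recording, a rule for unscheduled values, and baseline-relative grading of platelets and hemoglobin.

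The size is modest. No efficacy result is affected, individual cases stay visible, and the data set is small. The 4.8% to 19.0% range shows what per-cycle tables cannot distinguish under the assumed ALT values, attendance and timing; it is not an estimate of toxicity in this trial. The conclusion about the omission rests on the text alone.

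**What to change.** Add to SAP 10.6.3 a table of worst post-baseline grade per patient, preferably set against baseline grade, on the safety population.
- Parameters: key ones such as ALT, AST, bilirubin, ANC, platelets and hemoglobin. The protocol leaves the selection open, so the SAP should name them.
- Grading: CTCAE v5.0, with the table in protocol 7.4 for ANC, platelets and hemoglobin. Show patients who are not evaluable under its footnotes on a separate row. State the same exceptions in SAP 4.2 and 10.6.2.
- Values: all post-baseline results, with unscheduled ones explicitly included.

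Change-from-baseline summaries by cycle are optional, since the protocol does not promise them. If the sponsor prefers not to add the table, the SAP should record the departure from protocol 9.4.2 and the reason.

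The cost is a few extra tables and the programming of grades from data already collected. No assessment, visit or clinical rule changes.

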10.6.4 Physical Examinations

Analysis Set: Safety

Physical examination data will be listed for Screening visit.

A separate listing of patients with abnormal findings will also be presented.

10.6.5 Vital Signs

Analysis Set: Safety

Vital signs will include pulse rate, respiratory rate, blood pressure, and temperature (oral/axillary/tympanic). Weight will also be included here.

The baseline measurement is the last pre-treatment measurement taken on or before Cycle1 Day1.

Absolute values of Vital Signs data will be summarized descriptively (n, mean, median, standard deviation, minimum and maximum) per cycle. A listing will also be provided.

A separate listing of patients with abnormal vital signs findings will also be presented.

10.6.6 Electrocardiogram

Analysis Set: Safety

- The baseline measurement is the last pre-treatment measurement taken on or before Cycle1 Day1.
- Absolute values of ECG parameters [PR Interval, HR (heart rate), QT interval, QTcF (QT interval with Fridericia's correction), QRS Duration] as collected on CRF will be presented through n, mean, median, standard deviation, minimum, and maximum per cycle.
- A summary of abnormal ECG results will also be provided per cycle including baseline visit using frequencies and percentages.
- A listing of this data will also be provided.
- A separate listing for the abnormal ECG values will also be presented.

10.6.7 ECOG

Analysis Set: Safety

ECOG performance status, as reported in the eCRF, will be summarized per cycle with number and percentage for each status category. This data will also be listed.

The baseline measurement is the last pre-treatment measurement taken on or before Cycle1 Day1.

11. Protocol Deviations

Analysis set: FAS

A full list of protocol deviations for the study report will be compiled prior to database closure. All deviations will be reviewed by the Medical monitor prior to database closure. Each deviation

will be categorized as major and minor and a decision will be taken by the medical monitor whether to include the subject in a PP analysis population set.

Protocol deviations will be presented as number and percentage of patients with minor and major deviations in the study. This data will also be listed as appropriate.

12. Listings

In addition to all the listings mentioned above, separate listings will be presented for the following:

- Screened patients
- Eligibility review
- Study completion/Reasons for withdrawal of patient from the study
- Analysis populations
- Prior therapy
- Baseline Serology assessment
- Cancer diagnosis
- Disease assessment at Screening visit
- Follow-Up Cancer Overall Assessment
- Study drug exposure
- Study drug accountability
- Target lesion assessment
- Non-target lesion assessment
- Disease Response assessment
- Overall tumor assessment
- Pregnancy test
- Investigator Comments
- Patient visits

13. References

2. Hallek, M. *et al.* iwCLL guidelines for diagnosis, indications for treatment, response assessment, and supportive management of CLL. *Blood*. 2018;131(25):2745-2760
